2.2 Prior Specification for Combination Therapy

2.2.1 Marginal Prior for BMS-986207

Posterior information on $\log(\alpha_1)$ and $\log(\beta_1)$ from the monotherapy part of the study will be used as marginal BMS-986207 prior for combination with nivolumab. This prior information is not prespecified and will be continuously updated when additional DLT information from the monotherapy is available. In the simulation (see Section 3, the prior of BMS-986207 as described in [Section 1.2.1 \(Table 1\)](#) is used for illustration purposes because no real-time DLT data are available at this time.

2.2.2 Marginal Prior Derivation for Nivolumab Parameters ($\log(\alpha_2)$, $\log(\beta_2)$)

Similar to BMS-986207 monotherapy in the monotherapy phase, the logistic model for nivolumab is as follows:

$$\text{logit}(q_j) = \log(a_2) + \beta_2 \log(\frac{d_{2j}}{d_2^*}),$$

where q_j is the probability of toxicity at dose level d_{2j} . Note that the a_2 and $\{3_2\}$ parameters are assumed positive, and d_2^* is the reference dose for nivolumab.

The toxicity profile of nivolumab has been studied in several studies. A bivariate normal prior for the nivolumab model parameters ($\log(\alpha_2)$, $\log(\beta_2)$) was obtained by extracting a posterior of nivolumab using DLT and safety data from the Study CA209003, which is used later as the meta-analytical-predictive (MAP) prior for nivolumab.

The MAP prior for the model parameters ($\log(\alpha_2)$, $\log(\beta_2)$) was obtained in the following steps.

First, a prior distribution for nivolumab was developed:

- The median DLT rate at the reference dose (3 mg/kg every 2 weeks) was assumed to be 10%, that is, mean($\log(\alpha_2)$) = $\text{logit}(1/10) = \log(1/9) = -2.197$.
- A doubling in dose was assumed to double odds of DLT, that is, mean($\log(\beta_2)$) = 0.
- The standard deviation of $\log(\alpha_2)$ was set to 2, and the standard deviation of $\log(\beta_2)$ to 1, which allows for considerable prior uncertainty for the dose-toxicity profile.

- The correlation between $\log(\alpha_2)$ and $\log(\beta_2)$ is assumed to be 0 (assuming independence of $\log(\alpha_2)$ and $\log(\beta_2)$).
- In addition, heterogeneity between the historical study and current study was incorporated using a meta-analytic predictive approach by defining between-trial standard deviations τ_1 and τ_2 for $\log(\alpha_2)$ and $\log(\beta_2)$, respectively. The between-trial variability is assumed to be moderate. Therefore, τ_1 and τ_2 were set to follow a log-normal distribution, with mean $\log(0.25)$ and $\log(0.125)$, respectively, with a common standard deviation $\log(2)/1.96$.

With this prior, the clinical trial data below (Table 2) were used to generate the posterior for nivolumab, which is then used as the MAP prior for this study (Table 3).

Table 2: Data from Single-agent Nivolumab Study CA209003

Dose of Nivolumab (mg/kg)	Every 2 Weeks	
	No. of DLTs/No. of Evaluable Patients in the Escalation Phase	
0.1		0/3
0.3		0/3
1		0/3
3		0/3
10		1/6

Abbreviation: DLT = dose limiting toxicity.

Table 3: Marginal Prior Distribution for Model Parameters for Nivolumab (ie, Posterior from MAP Method)

Parameter	Means	Standard Deviations	Correlation
$\log(\alpha_2), \log(\beta_2)$	(-3.269, -0.152)	(1.186, 0.771)	-0.369

Note: Nivolumab prior information was based on a milligram-per-kilogram dosing instead of flat dosing. If real pharmacokinetic (PK) data from this study show difference from the milligram-per-kilogram assumption, the nivolumab prior will be revisited and modified accordingly.

2.2.3 Prior for Interaction Parameters for Joint Toxicity of BMS-986207 and Nivolumab Combination

A gamma prior distribution for the interaction parameter γ_1 is derived to reflect the current uncertainty about the toxicity profile of the combination of BMS-986207 and nivolumab. Although no PK drug-drug interaction is expected, the possibility of a significant positive interaction between BMS-986207 and nivolumab cannot be totally excluded. The interaction parameter γ_1 was chosen accordingly but with a degree of uncertainty to allow for the possibility that the interaction may be positive or negative. Therefore, the following assumptions are made for the interaction parameter:

- γ_1 follows a gamma distribution and with a mean centered at 1.1, which means the combination of 2 agents is likely to have only a small synergistic effect.
- The 97.5 percentile of γ_1 is $\log(3)$, that is, a 3-fold increase in odds of DLT due to the interaction over independence at the starting dose of the combination.

This model assigns the highest probability to there being small synergistic interaction and also allows for the potential of larger synergism of the toxic profiles. It also does not completely ignore the possibility of antagonism because there is a 40% prior probability that γ_1 is less than 1.

3 BLRM DECISION RULE FOR DOSE ESCALATION AND SIMULATION

Dose escalation recommendations for BMS-986207 monotherapy and in combination with nivolumab will be based on the inference from the Bayesian posterior and the probability that the true DLT rate for each dose lies in 1 of the following categories:

- [0%, 16%) under-dosing
- [16%, 33%) targeted toxicity
- [33%, 100%] excessive toxicity

These boundaries are similar to the toxicity boundaries used by a rule-based design (ie, 3 + 3 design) in that a minimum is set at 16% (~ 1 in 6) DLT rate and a maximum at 33% (~ 2 in 6) DLT rate. Following the principle of EWOC, dose recommendations for the next cohort will be based on the Bayesian model after DLT information becomes available during the DLT period, accounting for all of the available data from the administered doses, and the candidate doses are the ones fulfilling the overdose criterion that there is less than 30% chance of excessive toxicity. Only the candidate doses will be considered for the next cohort. While the Bayesian model will use DLT information from the DLT period only, clinical assessment will take into consideration of the totality of available data including PK/ [] from all treated participants.

Stopping Rules:

The following is the general stopping rules of BLRM (-Copula) during Dose Escalation:

- If all of 30 DLT evaluable participants are treated.
- If all of the current pre-specified doses are considered intolerable according to the pre-specified cutoff (ie, EWOC criteria), then the model will recommend stopping the current dose level and a new dose level lower than the current lowest dose level will need to be identified.
- The maximum number of participants in a dose level will be 12. This limit is set to avoid instances in which the model could recommend adding subjects indefinitely to a specific dose level due to uncertainty in the tolerability profile.
- If, for a specific dose level, 6 subjects have been treated and the chance of determining that the dose level to be the “target” dose is > 50%, then the model will suggest to stop and declare the current dose level to be MTD.
- **Model-recommended MTD:**
- The MTD is the dose that satisfies the following 3 conditions:

- (1) The empirical posterior probability that the ‘DLT rate of 16% -< 33%’ is greater than 50%,
- (2) This probability needs to be the largest among the dose levels that satisfy the EWOC condition (ie, the probability that ‘DLT rate $\geq 33\%$ ’ must be less than 30%);
- (3) Minimum number of participants (ie, 6), were treated at this dose level.

Final MTD/RP2D:

The final recommended MTD/RP2D will be based on the recommendation from the BLRM/BLRM-copula and overall clinical assessment of all available safety, PK/█ and efficacy data. Lower doses of BMS-986207 may be tested if none of the planned doses are found to be tolerable as monotherapy or in combination with nivolumab. Such decisions will be made after discussion and agreement between the investigators and the BMS Medical Monitor.

3.2 Simulation Parameters

One thousand trial simulations were used for each scenario. All simulations were run using EAST 6.3.1® software for BLRM model for BMS-986207 monotherapy and in-house developed code via R and Openbugs for BLRM-copula method for BMS-986207 in combination with nivolumab. The number of subjects to be treated in each cohort in a specific dose level and the stopping rules used to declare MTD are defined as:

- Fixed cohort size: 3
- Probability of overdosing: < 30%
- Probability of achieving the target toxicity: > 50%
- Maximum number of participants treated: 30
- Minimum number of participants treated at a given dose level in order to declare MTD: 6
- Maximum number of participants at a dose: 12

The provisional dose levels for BMS-986207 monotherapy are 80-1600 mg. For the combination therapy, nivolumab is fixed at 240 mg flat dose for q2w.

3.3 Operating Characteristics

Section 3.2.1 demonstrates operating characteristics of BLRM for monotherapy and Section 3.2.2 demonstrates operating characteristics of BLRM-copula for combination therapy accounting for joint toxicity of the combination therapy.

3.3.1 *Operating Characteristics of BLRM for Monotherapy*

Three scenarios were investigated by selecting (1) dose-DLT relationship derived by prior, (2) narrow safety window in order to explore how EWOC limits the risk of exposing participants from a toxic dose level, and (3) all doses above the target toxicity.

Table 4: Simulation Results of BLRM for Monotherapy

Scenario	BMS-986207 Dose	80	240	800	1600	MTD not selected (%)	Fitted MTD	Toxicity Observed (%)	Avg # Pts
	% DLT	5	10	20 ^a	30 ^a				
By prior	% MTD	0.9	18.1	51.7	28.3	1.0	1384	17.9	19.9
	# Pts	3.6	4.8	7.2	4.3				
	# DLTs	0.2	0.3	1.4	1.3				
	% DLT	5	10	20 ^a	80				
Narrow safety window	% MTD	0.7	26.2	71	0.3	1.8	1063	21.5	19.3
	# Pts	3.6	5.4	8.5	1.8				
	# DLTs	0.2	0.4	1.7	1.5				
All high	% DLT	50	60	75	80	93.3	30	62.0	5.6
	% MTD	5.7	1.0	0	0				
	# Pts	4.7	0.5	0.4	0.02				
	# DLTs	2.4	0.3	0.3	0.02				

% DLT, true DLT rate; % MTD, proportion of the dose selected as the MTD; # Pts, average number of participants by assuming 3 participants for skipped dose level where the true toxicity rate is below the target rate; # DLTs, average number of DLTs by assuming no DLT for skipped dose level where the true toxicity rate is below the target rate; Fitted MTD: fitted MTD at 30% as the target toxicity rate; % toxicity observed, average proportion of DLTs given the doses were tried

^a Doses with true target toxicity within the target toxicity interval [16%, 33%)

The average sample size was no more than 20 participants. The results for the scenarios of narrow safety window and all high show how the EWOC principle limits the risk of exposing participants from a toxic dose level. Overall, the scenarios illustrated above demonstrate that the model performs well in the hypothetical scenarios investigated by correctly identifying the MTD at least 71% of the time while limiting participants from receiving excessive/unacceptable toxic dose levels.

3.3.2 *Operating Characteristics of BLRM-copula for Combination Therapy*

Three hypothetical scenarios were investigated: (1) additive joint toxicity; (2) toxicity rates 25% higher than the additive scenario; (3) toxicity rates 50% higher than the additive scenario;

Table 5: **Simulation Results of BLRM-copula for Various Doses of BMS-986207 in Combination with Nivolumab 240 mg q2w**

Scenario	BMS-986207 Dose	80	240	800	1600	MTD not selected (%)	Fitted MTD	Toxicity Observed (%)	Avg # Pts
Additive	% DLT	10	14	25 ^a	40				
	% MTD	3.9	30.3	51.4	11.2	3.2	1335	20.0	19.9
	# Pts	4.3	5.0	8.4	2.2				
25% higher	#DLT	0.4	0.7	2.0	0.9				
	% DLT	13	18 ^a	32 ^a	50				
	% MTD	8.0	39.8	43.4	2.6	6.2	1019	30.0	18.4
50% higher	# Pts	4.8	5.8	6.7	1.1				
	#DLT	0.6	1.0	2.0	0.6				
	% DLT	15	21 ^a	38	60				
	% MTD	10.8	49.8	27.5	0.5	11.4	788	30.0	17.2
	# Pts	5.1	6.2	5.3	0.6				
	#DLT	0.8	1.3	2.0	0.3				

% DLT, true DLT rate; % MTD, proportion of the dose selected as the MTD; #DLT, average number of DLTs; MTD not selected: dose was below lowest dose or above highest dose; Fitted MTD: fitted MTD at 30% as the target toxicity rate and the dose range falls into the target toxicity range of [16%, 33%]; Toxicity observed: Average proportion of DLTs out of all simulated trials; # Pts, average number of participants

^a Doses with true target toxicity within the target toxicity interval [16%, 33]

The average sample size was no more than 20 participants. The results show how the EWOC principle limits the risk of exposing participants from unacceptable toxic dose levels, eg, 50% or above. Overall, the scenarios illustrated above demonstrate that the model performs well by correctly identifying the MTD ranging from 50% to 83% in the hypothetical scenarios investigated while limiting participants from receiving unacceptable toxic dose levels

4 BLRM INTERIM MONITORING CASE STUDY TO ILLUSTRATE PROVISION OF DOSE RECOMMENDATIONS DURING DOSE-ESCALATION

[figure not shown]
In order to provide a comprehensive view of the dynamics of the models, different hypothetical scenarios exploring all possibilities are examined. For the simplicity of illustration purposes, a static cohort size of 3 subjects is applied for dose levels 80 mg, 240 mg, 800 mg and 1600 mg in the BMS-986207 monotherapy and for the dose level 80 mg in the combination setting. This cohort size could vary during the actual clinical trial, and the BLRM (-Copula) models are designed to fit various different cohort sizes, adaptively. In general, there are 4 possible scenarios for a specific dose level, which are 0 DLT observed in 3 total subjects in that cohort (denoted as 0/3), 1 DLT

observed in 3 subjects (1/3), 2 DLTs observed in 3 subjects (2/3), and 3 DLTs observed in 3 subjects (3/3).

During interim monitoring, posterior probabilities will be updated when there is new DLT information available. The following three visualization plots will be produced to reflect the real time dose-DLT relationship, to quantify benefit (in the form of target dosing) and risk (in the form of overdosing and underdosing) during model's recommendation process, and to facilitate clinical team's interpretation of the model recommendations for the final decision making:

- Dose-DLT profile for the doses ranging between 0 mg and 1600 mg (Figure 1).
- Stacking histograms displaying predictive probabilities on DLT rates classified into 3 different categories (Underdosing, Target dosing and Overdosing) (Figure 2).
- Box plots summarizing the Markov Chain Monte Carlo (MCMC) samples of predicted DLT rates for the 5 pre-specified dose levels (Figure 3).

Figure 1: Updated dose-DLT profile after incorporating prior information and all previous DLT information up to 80 mg (including all monotherapy DLT data for BMS-986207 up to 240 mg)

Interpretation and usage of Figure 1:

Figure 1 is a snapshot of an updated dose-DLT profile with DLT information available at dose level 80 mg for combination studies. The dose-DLT profile is captured with a continuous dose spectrum ranging from 0 mg to 1600 mg, which is a slice of the dose-DLT surface of the combination of two drugs with Nivolumab fixed at 240 mg. For each dose within the range, there is a corresponding distribution of the predicted DLT rates calculated from the posterior samples of the model parameters. This figure will be updated each time new DLT information becomes

[figure not shown]
available from the combination studies. Similar graphs will also be produced for the BMS-986207 monotherapy.

In [Figure 1](#), there are 3 different quantiles (2.5%, 50%, and 97.5%) plotted to characterize the current trend of the toxicity profile (as shown by the 50% quantile), as well as the variation of the dose-DLT profile (as shown by the 2.5% percentile and the 97.5% percentile), according to the accumulation of DLT data from all previous and current dose levels. The toxicity boundaries (0.16 and 0.33) are illustrated in two dotted horizontal lines to benchmark the way in which the dose-DLT profile is trending.

Intermediate dose levels can be identified using different boundary cutoffs. For example, using the 50% percentile curve (green highlight), which represents the nearly average DLT distribution for each dose level, the 300 mg could be a potential intermediate dose level corresponding to the lower pre-specified DLT rate boundary of 0.16, and the 1600 mg could be a fitted MTD dose level associated with the upper boundary of 0.33.

Moreover, if all of the current pre-specified doses are considered intolerable (overdosing probabilities > 0.3 for combination therapy, a case not shown on the current [Figure 1](#)), the model will recommend to stop the current dose level, and the clinical team can leverage the current updated dose-DLT curve to pinpoint a new dose, which is lower than pre-specified lowest dose (80 mg) by using the DLT rate boundaries.

Figure 2: **Updated stacking histogram after incorporating prior information and all previous DLT information up to 80 mg (including all monotherapy DLT data up to 240 mg for BMS-986207) to classify predicted DLT rates into 3 categories (Underdosing, Target Dosing and Overdosing)**

Interpretation and usage of Figure 2:

[figure not shown]
[Figure 2](#) is a snapshot of stacking histogram with DLT information available at dose level 80 mg for the combination studies. This figure will be updated each time new DLT information becomes available in the combination setting. Similar graphs will also be produced for the BMS-986207 monotherapy.

When recommending the next dose level, the model will first exclude doses that are intolerable (with overdosing probabilities $> 30\%$, the rate that has been specified for BMS-986207 in combination with nivolumab). Among those qualified candidate doses that are considered “tolerable”, the model will select the dose that maximizes the probability of being within the target toxicity range (DLT rate of 16% up to 33%).

As illustrated in [Figure 2](#), when there is 0 DLT observed out of 3 subjects for the dose level 80 mg and 1 DLT out of 3 subjects for the dose level 240 mg, the distribution of predicted DLT rates will be characterized into possibilities falling into 3 different categories. First, dose levels of 800 mg and 1600 mg for BMS-986207 are excluded according to the higher-than-cutoff (0.3 for combination therapy) overdosing probabilities (0.364 for 800mg and 0.503 for 1600mg). Among the remainder of tolerable dose levels (80 mg and 240 mg), the BLRM-Copula model recommends the dose that maximizes the probability of being within the target dosing interval. Therefore, the model’s recommendation would be to escalate to 240 mg, which is associated with the highest target dosing probability of 0.342 compared with that of 80 mg (0.231).

Similarly (although not shown on [Figure 2](#)), according to the rules specified above, the model could possibly recommend to de-escalate to a lower dose level than current treated dose level, extend the current dose level, or even recommend to stop and identify a new dose level lower than 80mg, the lowest pre-specified dose level. Please refer to description of [Figure 1](#) for details on how to specify the new dose levels.

Figure 3: Updated box plot after incorporating prior information and all previous DLT information up to 80 mg in combination setting (including all monotherapy DLT data up to 240 mg for BMS-986207) for pre-specified dose levels

Interpretation and usage of Figure 3:

Figure 3 is a snapshot with DLT information available at dose level 80 mg for the combination setting. The dose-DLT distributions calculated from the posterior samples of the model parameters are characterized in the format of boxplots for the pre-specified dose levels. This figure will be updated each time there is new DLT information available. Similar graphs will also be produced for the BMS-986207 monotherapy.

This plot supplements the information provided in [Figure 1](#). It allows for a more in-depth and focused visualization of general trend of dose-DLT relationship, as well as the magnitude and variability in the DLT rates for each pre-specified dose level.

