10. STATISTICAL CONSIDERATIONS

10.1 Sample Size Determination

10.1.1 *Dose Escalation*

During the dose escalation phase, an adaptive dose escalation scheme (BLRM for monotherapy and BLRM-copula for combination therapy) employing the escalation with overdose control (EWOC) principle will be used. The method is fully adaptive, makes use of all the information available at the time of each dose assignment, not just data from the current dose level, and directly addresses the ethical need to control the probability of overdosing. The targeted toxicity rate in this study is in the range of [16%, 33%). The boundary is similar to the toxicity boundary used by a rule-based design (ie, 3 + 3 design) in that a minimum is set at 16% (~ 1 in 6) DLT rate and a maximum at 33% (~ 2 in 6) DLT rate. The use of the EWOC principle limits the risk of exposing patients in the next cohort to an unsafe dose by ensuring the posterior probability of the DLT rate exceeding 33% at any dose is capped at 30%.

The maximum number of participants treated will be 35 for each dose escalation part (BMS-986207 monotherapy [Part 1A], BMS-986207 in combination with nivolumab [Part 1B]). However, simulation studies with various scenarios show that the expected number of DLT-evaluable participants is no more than approximately 20. ([Appendix 12](#)).

Approximately 3 participants will be treated at the starting dose levels of BMS-986207 or BMS-986207 in combination with nivolumab. While the BLRM/BLRM-copula will use DLT information from the DLT period only, clinical assessment will take into consideration of the totality of available data including PK/█ from all treated participants encompassing monotherapy and combination therapy, in assigning a dose level for the next cohort of 3 participants. At least

6 DLT-evaluable participants will be treated at the MTD. At most 12 DLT-evaluable participants will be treated at each dose level. Additional participants (up to a total of 15) may be treated at or any dose level below the estimated MTD for further evaluation of safety, PK, [REDACTED] parameters as required.

The model-recommended MTD is the dose that satisfies the following three conditions:

- 1) The empirical posterior probability that the “DLT rate of 16% - <33%” is greater than a pre-specified value (i.e., 50%);

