1.2.1 Prior Derivation for BMS-986207 Parameters ($\log(a_1)$, $\log(\beta_1)$)

A weakly informative prior will be used for parameters (a_1 , β_1) for BMS-986207 to reflect the potential of the different toxicities of BMS-986207 and allow for considerable prior uncertainty.

Further details are provided below.

Weakly Informative Prior

- The median DLT rate at the reference dose (BMS-986207 at 1600 mg qd) was assumed to be 30%, that is, mean ($\log(a_1)$) = $\text{logit}(0.3) = \log(0.3/(1-0.3)) = -0.847$.
- A doubling in dose was assumed to double the odds of DLT, that is, mean($\log(\beta_1)$) = 0.
- The standard deviation of $\log(a_1)$ was set to 1.53 using the following steps:

- If the toxicity probability range was set to be [1%, 99%], then the toxicity interval would be $\text{logit}(0.99) - \text{logit}(0.01) = 9.19$.
- To cover 99.7% of the variance, the toxicity interval will cover $6 * \text{sd}(\log(a_1))$, which gives us $\text{sd}(\log(a_1)) = 9.19/6 = 1.53$.

Correspondingly, the standard deviation of $\log(\{3_1\})$ was set to 1, which allows for considerably larger prior uncertainty for the dose toxicity.

- 1) The correlation between $\log(a_1)$ and $\log(\{3_1\})$ was set to 0.
- 2) $\log(a_1)$ and $\log(\{3_1\})$ follow a bivariate normal distribution.

Table 1: Prior Distribution for Model Parameters for BMS-986207

Parameter	Means	Standard Deviations	Correlation
$\log(a_1)$, $\log(\beta_1)$	(-0.847, 0)	(1.53, 1)	0

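### The monotherapy operating characteristics in Appendix 12 Table 4 are not those of the MTD rule printed in the protocol, which requires P(target) above 50% and leaves roughly 27–57% of simulated trials without an MTD

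*Combined protocol and SAP*

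**What the plan says.** Two places define the model's MTD. Section 10.1.1 states: "The model-recommended MTD is the dose that satisfies the following three conditions". Appendix 12 Section 3 repeats it: "The MTD is the dose that satisfies the following 3 conditions". Both list the same three requirements, to be met together:

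1. the posterior probability of a DLT rate in [16%, 33%), called P(target) below, is above 50%;
2. that probability is the largest among doses meeting the overdose-control (EWOC) limit, meaning a probability below 30% that the DLT rate is 33% or more;
3. at least 6 participants were treated at the dose.

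Appendix 12 Section 3.2 puts the same threshold among the simulation settings used to declare an MTD: "Probability of achieving the target toxicity: > 50"%. It also sets cohorts of 3, at most 12 participants at a dose and at most 30 in total.

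Table 4 (Section 3.3.1) reports no MTD in 1.0% of trials (scenario by prior), 1.8% (narrow safety window) and 93.3% (all doses too toxic). The text below it concludes that the model performs well, "correctly identifying the MTD at least 71% of the time".

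**The concern.** An escalation can reach 12 participants at the recommended dose, or 30 overall, while P(target) is still at or below 50% everywhere. Condition 1 then fails and the printed rule names no MTD. The documents do not say what happens instead. Appendix 12 Section 3 foresees the situation, since it explains the 12-per-dose limit as a guard against the model adding participants indefinitely because tolerability remains uncertain.

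If such endings are common, non-selection of 1–2% cannot come from the printed rule. Establishing the MTD/RP2D is part of the primary objective for Parts 1A, 1B, 2A and 2B, and Table 4 is the evidence offered that the monotherapy design can do it. A reader would credit the written rule with performance that belongs to another one.

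**Working it through.** **The plan's own figures.** Table 4 is internally consistent. By prior: 0.9 + 18.1 + 51.7 + 28.3 + 1.0 = 100.0. Narrow window: 0.7 + 26.2 + 71 + 0.3 + 1.8 = 100.0. By prior, 800 and 1600 mg both lie in the target interval (true rates 20% and 30%), so correct selection is 51.7 + 28.3 = 80.0%. In the narrow window only 800 mg does, giving 71%. The smaller value is the 71% in the text.

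**Inputs** (Appendix 12 Sections 1.1, 1.2.1, 3 and 3.2, and Table 4):
- Model: logit p(d) = log a + β·log(d/1600).
- Prior: "The median DLT rate at the reference dose (BMS-986207 at 1600 mg qd) was assumed to be 30"%, so the mean of log a is log(0.3/0.7) = −0.847, with SD 1.53. "A doubling in dose was assumed to double the odds of DLT", so the mean of log β is 0, with SD 1. Correlation is 0.
- Doses 80, 240, 800 and 1600 mg, starting at 80 mg.
- True DLT rates 5/10/20/30% (by prior), 5/10/20/80% (narrow), 50/60/75/80% (all high).

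**Posterior.** For n_i treated and y_i DLTs at dose i, the posterior is proportional to prior × Π p_i^y_i (1 − p_i)^(n_i − y_i), evaluated on a grid. P(target) at a dose is the posterior mass with 0.16 ≤ p < 0.33. The next dose is the one with the largest P(target) among those with P(p ≥ 0.33) < 0.30.

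**One illustration.** Take 0/3 at 80 mg and 2/12 at 800 mg. This path skips 240 mg, and the Table 4 footnotes show that the simulation allowed for skipped doses. P(target) at 800 mg is 0.385, with an overdose probability of 0.052. At 1600 mg the overdose probability is 0.392, so EWOC excludes it. Thus 800 mg is the best eligible dose and is full, but 0.385 < 0.50 and no MTD can be declared there. With 3/12 instead, P(target) is 0.541 and the dose qualifies.

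**Printed rule, 6,000 trials per scenario (standard error about 0.6 points).** The documents do not say how the 12-per-dose cap ends or redirects a trial, so each reading was run. Percentage of trials with no MTD:

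| Handling of the 12-per-dose cap | Skipping allowed: by prior / narrow | No skipping: by prior / narrow |
|---|---|---|
| Trial ends when the recommended dose is full | 47.1 / 51.4 | 44.7 / 52.2 |
| Trial ends when any dose is full | 52.2 / 56.5 | 49.9 / 55.1 |
| Moves to the next-best dose | 27.0 / 30.9 | 31.3 / 34.5 |
| Table 4 | 1.0 / 1.8 | |

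Correct selection is highest with skipping and diversion: by prior 40.8 + 22.8 = 63.6%, narrow 55.4%. With skipping and any full dose ending the trial it is 27.9 + 12.9 = 40.8% and 33.9%. Repeat runs of 1,500 to 2,000 trials per variant widen the ranges to about 39–66% and 33–57%. No variant with the printed caps reaches 80% or 71%. Even with no per-dose cap and 60 participants, non-selection is 10.7% and 17.1%.

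**Relaxed rule.** Here 50% only stops a trial early. Otherwise the eligible dose with at least 6 treated and the largest P(target) is taken. With skipping, and the trial ending when the recommended dose is full:

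| | Simulated | Table 4 |
|---|---|---|
| No MTD: by prior / narrow / all high (%) | 1.2 / 1.5 / 93.9 | 1.0 / 1.8 / 93.3 |
| Selection at 80/240/800/1600 mg, by prior (%) | 0.7 / 21.0 / 50.3 / 26.8 | 0.9 / 18.1 / 51.7 / 28.3 |
| Selection at 80/240/800/1600 mg, narrow (%) | 0.8 / 30.4 / 67.1 / 0.2 | 0.7 / 26.2 / 71 / 0.3 |
| Participants: by prior / narrow / all high | 20.7 / 19.9 / 6.1 | 19.9 / 19.3 / 5.6 |

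Non-selection stays at about 1–2% across variants, except 2.6–4.6% when any full dose ends the trial. The match is close but not exact. For 67.1% (6,000 trials) against 71% (1,000 trials), the standard error of the difference is √(0.71·0.29/1000 + 0.671·0.329/6000) = 1.56 points, so the gap of 3.9 points is about 2.5 standard errors. Across variants the narrow scenario gives about 59–69%.

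**The case against.** The strongest reply is that 50% was only ever a stopping trigger. The stopping rules in Appendix 12 Section 3 do present it that way: once 6 are treated and the target probability exceeds 50%, stop and declare. The Table 5 footnote counts a trial as non-selecting only when the dose falls below the lowest or above the highest level, with no category for failing the 50% condition. This stands as a likely account of what was simulated. It does not rescue the text, because the MTD definition that follows the stopping rules, and its copy in Section 10.1.1, make 50% a necessary condition.

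Some limits on the evidence also stand. The monotherapy runs used EAST 6.3.1, whose selection step is not shown, so the simulated rule is inferred. The all-high scenario checks only the EWOC stop, not the 50% condition. An interim value below 0.50 proves little by itself: 0/3, 1/6 and 1/6 at 80, 240 and 800 mg gives 0.47, but that trial continues, and 2/12 at 800 mg would bring it to about 0.52.

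The practical stakes are modest by this amendment. Section 3.2.1.4 already reports 42 monotherapy and 30 combination participants, and Part 1C uses a different design (BOIN).

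**Conclusion.** The point holds as a mismatch between rule and table. Under the printed conditions, about 27–57% of trials in the two scenarios with a target dose end without a model MTD, against 1.0% and 1.8% in Table 4. Correct selection is about 39–66% and 33–57%, against 80% and 71%. This rests on the printed prior, doses and caps. The width comes mostly from the unstated handling of the 12-per-dose cap, so the ranges are not strict bounds.

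Three stronger readings are tempting and not supported:
- A reader might infer that the 71% sentence is an arithmetic slip. It agrees with Table 4; the table itself does not reflect the printed rule.
- A reader might infer that the RP2D will rest on discretion more often than the protocol admits. The protocol gives no such frequency, and Section 10.1.1 and Appendix 12 Section 3 always combine the model's recommendation with overall clinical assessment.
- A reader might infer a failure of overdose control. EWOC governs dose assignment and is the same under both rules.

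Table 5 was not re-simulated, so nothing is claimed about its figures.

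**What to change.** Reconcile Section 10.1.1, Appendix 12 Sections 3 and 3.2, and Table 4 so that they describe one procedure. There are two ways:

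- State the end-of-trial selection rule that was actually simulated, including what is declared when the 12-per-dose or 30-participant limit is reached without P(target) above 50%, and label the 50% condition accordingly.
- Keep the three conditions, re-run the simulations, and restate Table 4 and the sentence drawn from it.

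Either way, say how the 12-per-dose cap and dose skipping were handled, and check Table 5 and its summary against the same rule. The first route costs wording plus confirmation from the simulation settings. The second costs a re-run and probably less favourable stated performance.
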